10.4.1 Dose-response Candidate Curves

The MCP-Mod approach was created for dealing with model-uncertainty at the study design stage, by pre-specified set of candidate dose-response curves, combining principles of multiple comparisons with modeling techniques (Bretz et al., 2005). For this study, the candidate dose-response curves were selected based on prior knowledge of SPD489 dose-response, and assumptions on fixed-doses effects (placebo, SPD489 5, 10, 20, and 30 mg). The assumed family of plausible dose-response curves consists of linear, E_{max} , and logistic relationships, with appropriate parameters, covering the dose ranges of 0mg (placebo) to 30mg of investigational product. The candidate models and their figures are presented below.

| Family of the Curves | Candidate Dose-response Curves |
|----------------------|--|
| Linear | $-0.4 \times d$ |
| E_{max} | $-19.5 \times d / (15.0 + d)$ |
| Logistic | $0.5 - 13.5 / \{1 + \text{Exp}[(10 - d) / 3]\}$ $0.3 - 13.6 / \{1 + \text{Exp}[(15 - d) / 4]\}$ |

Where d stands for dose levels, $d = 0, 5, 10, 20, 30$ mg.

10.4.2 Dose-response Relationship Evaluations

When the study completes, regardless at the interim analysis or at end of the study, using the MCP-Mod methodology (Pinheiro et al, 2006) and all cumulative available data, the dose-response relationship of SPD489 as measured by the change from baseline for ADHD-RS-IV Preschool Version Total Score will be evaluated on the DRAS, fitting with an optimized candidate curve to identify the minimum effect dose (MED).

The dose response modelling in MCP-Mod uses a nonlinear least squares routine to fit the data to each of the candidate curve. Each of the dose response shapes in the candidate set will be tested using an appropriate contrast T-statistic. Using of the multivariate t-distribution to determine a critical value for all of the contrast T-statistics controls the overall Type-I error rate. The maximum contrast test statistic will be used to select a dose response curve out of the set of significant curves, if there are any significant curves. If at least 1 of the specified candidate curve is selected, using a 2-sided significance level of 0.05, then for this selection process, dose response for SPD489 is established.

The dose response model will include sex (female vs. male), baseline ADHD subtypes and baseline ADHD-RS total scores as explanatory variables in the dose response analysis. The baseline ADHD-RS score will be a continuous covariate, whereas sex and ADHD subtypes will be factors.

The modeling results of the candidate curves will be tabulated that include T-statistic and corresponding adjusted p-values for each curve. Also parameters estimated for the final dose response relationship curve, and figures showing the dose response relationship will be presented. Fitted significant curves with ADHD-RS total score change from baseline data will be displayed as well.

10.4.3 Minimum Effective Dose

If a significant dose-response relationship can be established using the maximum contrast test statistic, then a clinically relevant threshold, – 5.6 reduction from baseline in ADHD-RS-IV Preschool Version Total Score, which derived from assumed minimum clinical meaningful effect size of 0.40 and common standard deviation of 14, will be used for the MED derivations. The 95% CI of the MED will be bootstrapped, that is, subjects will be sampled with replacement within the randomized treatment group for resampling, and the full MCP-Mod procedure will be applied to the resampled data, producing a bootstrap sample of MED values. The 95% CI for the MED correspond to the 2.5% and 97.5% quantiles of the bootstrap samples.

By default, MCP-Mod reports the MED as missing if any of the significant curves fails to converge or if an estimate cannot be determined from a particular converged model.

If an MED estimate cannot be determined from the selected significant curve, then available MED estimates from other converged models will be used to calculate an MED using the average AIC method.

10.4.4 Additional Analyses

A line-plot of mean change from baseline with 95% CI for each randomized treatment group will be generated.

Each SPD489 arm will be compared with placebo in ADHD-RS-IV Preschool Version Total Score change from baseline using MMRM. The comparisons will be conducted in a sequential order for adjusting for the multiplicity, which will test the highest dose level, 30 mg, first. The model structure will be similar to the primary efficacy analysis. However, this analysis is not powered for the comparisons.

A sigmoid nonlinear E_{max} model ([MacDougall, J. 2006](#)) below will be fitted, and the sigmoid E_{max} model curve will be plotted.

$$R_i = E_0 + \frac{D_i^m \times E_{max}}{D_i^m + ED_{50}^m} + \varepsilon_i$$

Where i = the subject indicator; R_i = dose response for subject i that measured as ADHD-RS-IV Preschool Version Total Score change from baseline; E_0 = the dose response when dose strength is 0 mg (placebo); D_i = the dose level for subject i ; m = the slope factor determining the steepness of the dose response curve ($m > 0$); E_{max} = the maximum possible effect for the investigational product; ED_{50} = The dose level, which produces half of E_{max} ; ε_i = the random error term for subject i .

For the E_{max} model evaluations, initial parameters will be set to $E_0 = 0$; $E_{max} = -19.5$; $ED_{50} = 15.0$ and $m = 3.17$. Where the m was calculated using the formula

$$ED_p = ED_{50} \left(\frac{p}{1-p} \right)^{1/m}$$

let $p = 0.9$, $ED_{90} = 30.0$.

The MCP-Mod methodology provides a flexibility of modeling for dose response relationship, while preserving the robustness to model misspecification associated with multiple comparison procedures (Bretz et al. 2005). However, if the MCP-Mod fails to converge to any pre-specified candidate curves, the sigmoid nonlinear E_{max} model, as a backup, will provide a dose response relationship. Using the relationship and clinically relevant threshold— 5.6 reduction from baseline in ADHD-RS-IV Preschool Version Total Score together, an approximately estimate of MED will be obtained.

10.5 Supportive Analyses

10.5.1 Subgroup Analysis

The subgroups considered for analyses will be sex (male, female), race (white, non-white), and ethnicity. There is no formal hypothesis testing is planned for the pooled SPD489 (10, 20 and 30 mg) dose group and placebo for the subgroup analysis.

ADHD-RS-IV total score and CGI-I data will be summarized descriptively for each subgroup that is defined above at each visit by pooled SPD489 (10, 20, 30 mg) and placebo group.

10.5.2 Other Analyses

The items in the ADHD-RS-IV Preschool Version will also be grouped into 2 subscales: hyperactivity/impulsivity (even-numbered items 2-18) and inattentiveness (odd-numbered items 1-17). Each subscale will be analyzed using a similar model as the primary efficacy endpoint and summarized descriptively at each visit by pooled SPD489 treatment group and placebo. A corresponding line graph of the LS means of change from baseline and associated 95% CI in ADHD-RS-IV Preschool Version subscale scores by pooled SPD489 treatment, placebo and visit will be presented.

The ADHD-RS-IV total score will be summarized descriptively at each visit by pooled SPD489 treatment and placebo.

The key secondary efficacy measurement, CGI-I, will also be analyzed using the proportion of subjects with an “improved” CGI-I measurement at endpoint. The CGI-I categories will be dichotomized into 2 categories: “very much improved” and “much improved” classified as “improved,” and all other assessed categories grouped together as “not improved.” The key secondary efficacy analysis will be conducted to compare pooled SHP489 treatment and placebo on the FAS for the “improved” rate using a Cochran-Mantel-Haenszel test stratified by CGI-S value at baseline.

Dichotomized CGI-I values will be summarized by visit and pooled SHP489 treatment and placebo. A corresponding bar chart showing the percentage of subjects improved by visit, pooled SHP489 treatment, and placebo group will be presented. CGI-I values and CGI-S values will be listed.

The CGI-I will be summarized descriptively at each visit by pooled SHP489 treatment and placebo.

11. SAFETY ANALYSES

The Safety Analysis Set based on either the interim analysis dataset that for the safety summary at interim analysis, or the interim analysis dataset together with the overrun if the efficacy criterion meets, or all cumulative data up to study completion, whenever it is appropriate, will be used to report the safety data.

Safety data will be summarized by SPD489 dose strengths, pooled doses and placebo. Safety variables include AEs, clinical laboratory variables, vital signs, physical examinations, Children's Sleep Habits Questionnaire (CSHQ), sleep diary, ECG, and C-SSRS variables. For each safety variable, the last value collected before the first dose of investigational product will be used as baseline for all analyses of that safety variable.

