#### **7.2.4.4 Vital Signs**

Measurements of oral or tympanic temperature and sitting respiratory rate will be performed at the screening visit (Visit -1) and Visit 6/ET only.

Measurements of sitting systolic and diastolic blood pressure and pulse will be performed at each visit to the site. Blood pressure, pulse, and respiratory rate will be determined after subjects have remained at rest for a minimum of 5 minutes.

Blood pressure will be determined by manual cuff (the same equipment and the same arm should be used throughout the study). A blood pressure cuff appropriate for the subject's arm length and girth should be used for all blood pressure measurements. The cuff should be approximately two-thirds the length/width of the subject's arm (from elbow to shoulder). All blood pressure measurements should be performed throughout the study using a manual cuff and should be performed by the same study center personnel (if possible) throughout the study. After 5 minutes of rest, three measurements should be obtained using the manual cuff with approximately 2 minutes in between each collection for blood pressure and pulse and report the average of the 3 measurements for each parameter. The 3 individual measurements and the averaged reading should be recorded in the source and CRF.

Any clinically significant deviations from Baseline (Visit 0) vital signs which are deemed clinically significant in the opinion of the investigator are to be recorded as an AE.

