#### 7.2.4.7 Electrocardiogram

A 12-lead ECG will be performed at the screening visit (Visit -1) and every post-baseline visit (Visit 1 to Visit 6/ET). Additionally, three ECGs taken approximately 5 minutes apart will be collected at the baseline visit (Visit 0). The mean interval values of the 3 ECGs is used to establish the subject's baseline intervals. All ECGs will be performed after 5 minutes of rest using the central ECG provider's equipment and will be sent to the central ECG provider electronically.

The initial interpretation of the ECG, normal or abnormal, and clinical significance, will be performed immediately after collection by the investigator. The ECG tracing will then be evaluated by a cardiologist at the central ECG reading vendor (Cardiocore) for analysis and returned to the site with a determination of normal or abnormal. Upon review of the report from Cardiocore, the investigator will re-evaluate the clinical significance of the ECG while taking into consideration all other safety data available for the subject.

Although a central ECG reader is being used for this study, the eligibility of the subject is based on the investigator's assessment of the ECG. If abnormal and significant results are observed following assessment by the central reader, the investigator, in consultation with the appointed CRO medical monitor, reconfirms subject eligibility to continue.

All ECGs transmitted to the central ECG reader will be analyzed. If the central ECG reader receives multiple ECGs, the first readable ECGs will be analyzed as the scheduled ECG. Every ECG transmitted to the central ECG reader will have corresponding CRF data collected. No ECG should be deleted by study site personnel. All ECGs must be transmitted to the central provider regardless of quality, results, or number of ECGs taken at a respective visit.

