^d An abbreviated physical examination, 12-lead ECG, and all clinical laboratory tests must be repeated and results reviewed by the investigator prior to the baseline visit (Visit 0) if more than 30 days have elapsed since the safety measurements at the screening visit (Visit -1) were collected. Results must be obtained and reviewed prior to determining eligibility.

^e Includes oral or tympanic temperature, sitting blood pressure, pulse, and respiratory rate. Measurements of blood pressure and pulse will be performed at each visit to the site. Measurements of temperature and respiratory rate will be performed at the screening visit (Visit -1) and Visit 6/ET only. Blood pressure, pulse, and respiratory rate will be

Table 1: Schedule of Assessments

| Period | Screening and Washout | | | Dose-titration | | | Dose-maintenance | | | Safety Follow-up |
|--------------------|-----------------------|------------------------|-----------------|----------------|-----------|-----------|------------------|-----------|-----------|------------------|
| | -1 (Screening) | Washout Telephone Call | 0 (Baseline) | 1 | 2 | 3 | 4 | 5 | 6/ ET | |
| Visit ^a | -4 to -1 | -1 | 0 | 1 | 2 | 3 | 4 | 5 | 6 | Telephone Call |
| Assessment Week | -4 to -1 | -1 | 0 | 1 | 2 | 3 | 4 | 5 | 6 | 7 |
| Assessment Day | -28 to -1 | | 0 | 7 | 14 | 21 | 28 | 35 | 42 | 49 |

determined after subjects have remained seated for a minimum of 5 minutes. Measurement of blood pressure and pulse will be collected 3 times (with approximately 2 minutes in between each collection) using a manual cuff. The average of each set of 3 measurements will be used to determine continued participation in the study. Blood pressure measurements should be taken prior to the collection of blood draws.

^f Height and weight to be measured without shoes.

^g BMI will be recorded at Screening for eligibility. BMI will be derived from height and weight during the course of the study for analysis.

^h Clinical laboratory tests will include hematology, chemistry, endocrinology, and urinalysis.

ⁱ Patients will have the option for blood draws to be collected by a home health care professional at their home. Home draws have a ± 1 day window from the study visit date, with the exception of the 6/ET home draw which has a -1 day window.

^j Three ECGs, taken approximately 5 minutes apart, are to be collected so that appropriate baseline intervals are established. Results must be reviewed prior to determining eligibility.

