Descriptive statistics (n, mean, SD, minimum, median, and maximum) for ECG variables (heart rate, PR interval, RR interval, QRS interval, QT interval, and QTc interval) and their changes from baseline at each assessment time point will be presented by treatment group. QTc interval will be calculated using both Bazett ($QTcB = QT/(RR)^{1/2}$) and Fridericia ($QTcF = QT/(RR)^{1/3}$) corrections; if RR is not available, it will be replaced with 60/hr in the correction formula. ECG interpretation will be summarized by visit (and Visit 6/ET) and treatment group. A shift table from baseline to each visit (and Visit 6/ET) for qualitative ECG results will also be presented.

All ECG values will be listed for the Safety Analysis Set.

Electrocardiogram variable values, include unscheduled visit, will be considered PCI if they meet either the observed value criteria or the change from baseline criteria listed in [Table 4](#). The number and percentage of subjects with post-baseline PCI values will be tabulated by treatment group. The percentages for the observed value criteria will be calculated relative to the number of subjects with at least 1 post-baseline assessment available per parameter and visit. The percentages for the change from baseline criteria will be calculated relative to the number of subjects with available baseline and at least 1 post-baseline assessment per parameter and visit. The numerator is the total number of subjects with at least 1 PCI post-baseline ECG value. A listing of all subjects with post-baseline PCI value will be provided including the subject number, site, baseline, and post-baseline PCI values.

Table 4: Criteria for Potentially Clinically Important ECG Values

| ECG Parameter | Unit | Observed Value | | Change from Baseline | |
|---------------|--------------|----------------|--|----------------------|--------------|
| | | Lower Limit | Higher Limit | Lower Limit | Higher Limit |
| ECG Result | - | - | Abnormal (core lab) and clinically significant from investigator | - | - |
| Heart Rate | Beats/minute | <55 | >130 | Decrease >15 | Increase >15 |

Table 4: Criteria for Potentially Clinically Important ECG Values

| | | | | | |
|---------------|------|---|--|---|-----------------------------------|
| PR Interval | msec | - | ≥ 200 | - | - |
| QT Interval | msec | - | ≥ 440 | - | ≥ 30 and < 60 ≥ 60 |
| QTcF Interval | msec | - | ≥ 440 and < 480 ≥ 480 and < 500 ≥ 500 | - | ≥ 30 and < 60 ≥ 60 |

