18.3 Repeated or Unscheduled Assessments of Safety Parameters

If a subject has repeated assessments before the start of investigational product, then the results from the final assessment made prior to the start of investigational product will be used as baseline. If end-of-study assessments are repeated or unscheduled, the last post-baseline assessment while on investigational product will be used for generating descriptive statistics. However, all post-baseline assessments will be used for PCI value determination and all assessments will be presented in the data listings.

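### Baseline ECG intervals: the protocol averages three Visit 0 tracings, the SAP's last-value rule taken literally uses only the third, and nothing reconciles the two

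*SAP*

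**What the plan says.** **Protocol.** Section 7.2.4.7 schedules three 12-lead ECGs about five minutes apart at Visit 0 and one at each later visit. Of the Visit 0 set it says: "The mean interval values of the 3 ECGs is used to establish" the subject's baseline intervals. The same section says that, if the central reader receives several ECGs, the first readable ones count as the scheduled ECG. On recording it says: "Every ECG transmitted to the central ECG reader will have corresponding CRF data collected". Section 9.9, on safety analyses, defines no ECG baseline.

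**SAP.** Section 11 names ECG among the safety variables and sets one rule for all of them: "the last value collected before the first dose of investigational product will be used as baseline for all analyses of that safety variable". Footnote j to the schedule in section 2.4 keeps the triplicate, saying the three ECGs "are to be collected so that appropriate baseline intervals are established", but does not mention averaging. Section 11.4 plans descriptive changes from baseline for the ECG variables. It also plans potentially clinically important (PCI) flags, which in Table 4 include QT, QTcF and QTcB increases of 30 to under 60 msec and of 60 msec or more. It gives no ECG-specific baseline. Section 17 declares no change to the protocol's analyses.

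**The concern.** The two documents give different recipes for the same quantity. A programmer working from the protocol averages three tracings. One working from SAP 11 keeps the most recent, which is the third. Each can cite a governing document, and the two will produce different change-from-baseline tables and different lists of flagged children.

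A triplicate is taken to reduce measurement error in the value against which every later tracing is compared. Using one tracing gives that up. Changes become more variable, and more children cross the 30 msec line by noise alone. For a stimulant in children aged 4 to 5 the QTc outlier table will be read closely, so its baseline should be fixed before unblinding and not chosen once the flag counts are known.

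**Working it through.** **1. Do the texts conflict?**

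| Question | Protocol 7.2.4.7 | SAP |
|---|---|---|
| How many Visit 0 tracings? | Three | Three (2.4, footnote j) |
| Which value is the interval baseline? | Mean of the three | Last pre-dose value (11) |
| Is ECG exempt from the general rule? | – | No exemption in 11 or 11.4 |
| Is a change declared? | – | None (17) |

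Blood pressure is also taken in triplicate but is not exposed in the same way, because protocol 7.2.4.4 puts the average itself on the record: "The 3 individual measurements and the averaged reading should be recorded in the source and CRF". For ECG the protocol mentions a record per tracing and no averaged record. On the visible text, then, the mean has to be derived, and the SAP does not say so.

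**2. How much could it matter?** The documents contain no figure to reproduce and no ECG standard deviation. Everything below is an illustration under assumed values and no drug effect.

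Model: reading = day effect with SD *v* + tracing error with SD *e*, both normal. Visit 0 has three tracings sharing one day effect. Each of six later visits has one tracing.

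- SD of change, last tracing as baseline: √(2v² + 2e²)
- SD of change, mean of three as baseline: √(2v² + 4e²/3)
- Per-visit flag rate: upper normal tail at 30/SD
- Any flag over six visits: 1 − E[Φ((30 + B)/√(v² + e²))⁶], where the baseline error B is normal with variance v² + e² (last tracing) or v² + e²/3 (mean of three)

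Example, v = e = 8 msec: √(128 + 128) = 16.00 and √(128 + 85.3) = 14.61. The tails at 30/16.00 = 1.875 and 30/14.61 = 2.054 are 3.04% and 2.00%, a per-visit excess of 1.0 point.

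Results for v = 8 msec, increase of 30 msec or more:

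| e (msec) | Per-visit excess (points) | Any flag, last tracing | Any flag, mean of three | Excess (points) |
|---|---|---|---|---|
| 2 | 0.04 | 2.46% | 2.32% | 0.1 |
| 4 | 0.2 | 4.13% | 3.45% | 0.7 |
| 6 | 0.5 | 7.39% | 5.69% | 1.7 |
| 8 | 1.0 | 12.26% | 9.29% | 3.0 |
| 12 | 2.4 | 24.54% | 20.05% | 4.5 |

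The any-flag column is by numerical integration. A simulation of 1,000,000 subjects per setting agrees to within about 0.1 point. The per-visit column matters because SAP 11.4 calculates change-based percentages "relative to the number of subjects with available baseline and at least 1 post-baseline assessment per parameter and visit".

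**3. Range.** With v = 4, 8 or 12 and e no larger than v, the any-flag excess runs from 0.0 to 3.0 points and the SD of change is 0.5% to 10% larger. An active arm has 195 × 5/26 = 37.5 children, so the upper end is 37.5 × 0.030 = 1.1 children. Outside that limit, e = 12 with v = 8 gives 37.5 × 0.045 = 1.7 children. With v = 4 and e = 12 the rates are 17.6% and 11.2%, an excess of 6.4 points or 37.5 × 0.064 = 2.4 children. At v = 8 the flag for 60 msec or more stays below 1% under either rule. At v = e = 12 it is 3.0% against 1.7%.

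**The case against.** The best defence is that SAP 11 is a generic sentence covering laboratory tests, questionnaires and ECG alike. Its purpose is to prefer Visit 0 to Screening, not to choose among tracings within a visit. The SAP presents itself as an elaboration of the protocol, repeats the reason for the triplicate and declares no change. The protocol's averaging sentence sits among study procedures, so silence in SAP 17 is weak evidence of an undeclared departure. The record layout and dataset specifications are not visible, and a mean may exist in the central reader's data.

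Much of this stands. The visit-level reading is sensible and may well be what was intended. But no SAP sentence says it, and the sentence that is there points to one reading. The documents do not show that a mean is recorded anywhere. The protocol's first-readable rule does not settle which tracing or tracings form the SAP baseline either.

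Three stronger inferences are tempting and should not be drawn:

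- *The qualitative shift table has no baseline rule.* SAP 11.4 says a shift table "for qualitative ECG results will also be presented", and a mean cannot supply its baseline. But the SAP 11 last-value rule, read literally, does supply a single reading for it.
- *Heart rate must be averaged too.* The protocol's sentence covers interval values and does not name heart rate. Averaging it is an option, not a requirement.
- *SAP 18.3 confirms that the last tracing overrides the mean.* For repeated pre-dose assessments it says "then the results from the final assessment made prior to the start of investigational product will be used as baseline", but its heading concerns repeated or unscheduled assessments. A scheduled triplicate need not fall under it.

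**Conclusion.** The inconsistency is real and minor. The protocol's interval baseline is a mean of three, the SAP's written rule gives one value, and no text joins them. The consequence is confined to the descriptive interval changes and the change-based QT, QTcF and QTcB flags: slightly more noise and a few more false flags of 30 msec or more.

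The figure of about 0 to 3 points for any flag over six visits rests on assumed SDs, normality, no drug effect, and tracing-to-tracing variation no larger than day-to-day variation. A larger within-session SD would raise it. A reader might infer that the safety comparison is biased. It is not: every arm has the same baseline rule, so the mean difference from placebo is unaffected. Observed-value flags, efficacy and type I error are untouched. All tracings are collected and all ECG values are to be listed, so no information is lost and the mean can be computed later.

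**What to change.** In SAP 11.4, as a stated exception to the last-value rule in SAP 11, define baseline for the ECG interval variables, and the QTc values derived from them, as the mean of the readable scheduled Visit 0 tracings, using those available if fewer than three. Word it to agree with the first-readable sentence in protocol 7.2.4.7, so that an extra tracing sent from Visit 0 does not enter the mean.

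The last-value rule can stay for the qualitative shift table. If the team also wants heart rate averaged, it should say so as its own choice. If a single-tracing baseline was in fact intended, SAP 17 should declare it.

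The cost is one SAP sentence before unblinding. No new data and no protocol amendment are needed.
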